12.2 Sample Size/Accrual Rate

Our target sample size will be 100 COVID-19 survivors. 50 participants will be randomized to the AKL-T01 intervention arm and 50 participants will be randomized to a waitlist control arm.

Our total enrollment to meet our target sample size of 100 participants will be 125. Based on previous research conducted at our institution, we anticipate ~20% of individuals will decide not to participate after meeting eligibility criteria.

As primary analysis will utilize linear mixed models (as implemented in lme4) to examine slope of symptom change, we utilized the simr package in R (4.0) to estimate power for the specified model assuming 50 participants per study arm in 100 simulated data sets. For standardized beta coefficient corresponding to Cohen's d of ~0.4, power exceeds 88% (95% confidence interval 80.0-93.6%) for the base case, and exceeds 80% under a range of conservative assumptions, with alpha=0.05 for the primary hypothesis test.

We expect enrollment to last approximately 12 months, yielding an accrual rate of ~10 participants per month.

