9.2.1 Title – Special Correlative Study #1

9.2.1.1 Assessment

9.2.1.2 Method of Assessment

9.2.1.3 Timing of Assessment

10. Measurement of Effect

Calculated for primary and secondary outcome measures, comparing the active intervention (AKL-T01; week 0 to week 6 for intervention arm) to the waitlist control (week 0 to week 6) using standard inferential statistical techniques and calculation of effect sizes. Formally, for primary and secondary outcomes, we will apply linear mixed effects models with fixed effects for treatment group as the between-subjects factor, time (week number) as the within-subjects factor, and group-by-time interaction. A random intercept will be included. Effect size will be reported in terms of group-by-time interaction (i.e., difference in slope of change between

groups). Despite the protection afforded by randomization, should potential confounding variables be identified from among baseline sociodemographic and clinical features, secondary analyses will incorporate fixed terms for those putative confounders in linear models.

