12.1 Study Design/Endpoints

We will test the hypothesis that patients receiving the AKL-T01 intervention will have significantly enhanced improvement in cognition and daily functioning, relative to a waitlist control group.

- 1) Our primary cognitive measure will be change in performance on a Digit Symbol Matching Task from baseline (pre-intervention) to week 6 (post-intervention) in all participants randomized to the AKL-T01 intervention arm or the waitlist control arm.
- 2) Our primary daily functioning measure will be change in score on the NeuroQOL Cognitive Function scale from baseline (pre-intervention) to week 6 (post-intervention) in all participants randomized to the AKL-T01 intervention arm or the waitlist control arm.

We will use analysis of variance (ANOVA) to test for differences in 1) Digit Symbol Matching and 2) NeuroQOL change scores across the intervention and control arms.

A secondary outcome analyses will use ANOVA to test for group differences in change in performance on the remaining cognitive tasks (Multiple Object Tracking, Digit Span Backwards, Simple RT, Choice RT, Letter Number Switch) and group differences in the WHODAS 2.0, our secondary measure of daily functioning.

We will use the Holm-Bonferroni method to correct for multiple comparisons. An intent-to-treat approach will be used in for all of the analyses above, including outcomes in participants who did not complete the intervention.

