12.4 Analysis of Endpoints

12.4.1 Analysis of Primary Endpoints

Our primary cognitive measure will be change in performance on a Digit Symbol Matching Task from baseline (pre-intervention) to week 6 (post-intervention) in all participants randomized to the intervention or control arm. Our primary daily functioning measure will be change in score on the NeuroQOL Cognitive Function scale from baseline (pre-intervention) to week 6 (post-intervention) in all participants randomized to the intervention or control arm. We will use analysis of variance (ANOVA) to test for differences in Digit Symbol Matching and NeuroQOL change scores across the two arms.

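### The plan names two different primary analyses for Digit Symbol Matching, a mixed-model slope and an ANOVA of week-6 change, and gives power only for the first

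*Combined protocol and SAP*

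**What the plan says.** Two sections point to a mixed model. Section 10 (Measurement of Effect) states that "for primary and secondary outcomes, we will apply linear mixed effects models" with group, "time (week number) as the within-subjects factor", their interaction and a random intercept. It adds: "Effect size will be reported in terms of group-by-time interaction". Section 12.2 calls this kind of model the primary analysis ("As primary analysis will utilize linear mixed models (as implemented in lme4) to examine slope of symptom change") and powers it: "For standardized beta coefficient corresponding to Cohen's d of ~0.4, power exceeds 88% (95% confidence interval 80.0-93.6%) for the base case".

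Two sections point to an ANOVA. Section 12.1 says: "We will use analysis of variance (ANOVA) to test for differences in 1) Digit Symbol Matching and 2) NeuroQOL change scores". Section 12.4.1, the section on analysis of the primary endpoints, says: "We will use analysis of variance (ANOVA) to test for differences in Digit Symbol Matching and NeuroQOL change scores across the two arms". Section 1.2.4 defines the primary endpoint as mean change from baseline to week 6 on Digit Symbol Matching, compared between arms as change scores.

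Sections 10 and 12.2 do not mention ANOVA. Sections 12.1 and 12.4.1 do not mention a mixed model. Nothing makes either one supportive.

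**The concern.** A change-score ANOVA uses one number per person, the week-6 score minus the baseline score. A slope model fits a straight line through every visit it is given. Section 10 frames the comparison as "week 0 to week 6 for intervention arm" and the same period for controls, but does not say whether weeks 2 and 4 enter, although Section 6.1.2.2 collects Digit Symbol Matching at both.

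The two also differ when a week-6 score is missing. The mixed model can keep the person's earlier visits. A change score cannot be formed without an imputation rule, and none is given. Section 3.2 itself foresees dropout among controls.

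Two things are at stake. The confirmatory test is not uniquely fixed in advance, so the same data could give two verdicts. And the reader has no power figure for the test that Section 12.4.1 names.

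**Working it through.** **Inputs from the documents.** 50 per arm; Cohen's d about 0.4; alpha 0.05; 100 simulated data sets (all Section 12.2). Visits at weeks 0, 2, 4 and 6 (Section 6.1).

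**Assumed, because the documents do not say.** Two-sided test; effect of 0.4 in raw SDs at week 6; complete data; raw SD of 1 at every visit; within-person correlation rho.

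**1. The plan's own figure.** The exact (Clopper-Pearson) interval for 88 of 100 is 79.98-93.64%, which is the stated 80.0-93.6%. So 88% is the simulation's point estimate for the mixed model. It cannot be reproduced from first principles, because Section 12.2 does not give the SD scale of d, the correlation or the visits simulated.

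**2. Equal correlation between visits, benefit growing linearly.** Variance of the six-week contrast between arms:
- Change-score ANOVA: 4(1 - rho)/50, 98 df.
- Random-intercept slope on weeks 0, 2, 4, 6: the squared deviations of week sum to 20, so 36 x 2(1 - rho)/(50 x 20) = 3.6(1 - rho)/50, 298 df.

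At rho 0.5 the variances are 0.0400 and 0.0360; at rho 0.775 they are 0.0180 and 0.0162. Noncentral-t power for a difference of 0.4:

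| rho | ANOVA | Slope, linear benefit | Slope, benefit complete by week 2 or only at week 6 |
|---|---|---|---|
| 0.5 | 50.8% | 55.6% | 47.3% |
| 0.7 | 72.5% | 77.4% | 68.5% |
| 0.775 | 83.9% | 88.0% | 80.5% |

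The last column follows from the slope's visit weights, -0.9, -0.3, 0.3 and 0.9. Effects of (0, 0.4, 0.4, 0.4) or (0, 0, 0, 0.4) both give a fitted six-week contrast of 0.36 instead of 0.4, so the order of the tests reverses. A rho of 0.775 was included because it returns the plan's 88% for the slope.

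If only weeks 0 and 6 enter, the deviations sum to 18. The slope variance is then 72(1 - rho)/(50 x 18) = 4(1 - rho)/50, the same as the ANOVA's.

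**3. How often the verdicts differ.** Both tests were run on the same simulated trials, 40,000 per setting. Under linear benefit, only the ANOVA or only the slope was significant in 3.4% + 8.2% = 11.6% of trials (rho 0.5) and 1.3% + 5.5% = 6.8% (rho 0.775). With full benefit by week 2 the figures were 7.9% + 3.5% = 11.4% and 6.1% + 2.0% = 8.1%. With no effect, at least one test was significant in 6.5-6.6% of trials.

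**4. Correlation that decays between visits (assumed AR(1), rho per two weeks).** With the same weights, the true variance of the slope contrast is 2(1.8 + 0.9rho - 1.08rho² - 1.62rho³)/50. The random-intercept model instead estimates about 3.6(1 - r)/50, where r is the average pairwise correlation, (3rho + 2rho² + rho³)/6.
- rho 0.8: true 0.0400, model 0.0217. SE ratio 0.737; type I error 2[1 - Φ(1.96 x 0.737)] = about 15%.
- rho 0.9: true 0.0222, model 0.0114. SE ratio 0.717; type I error about 16%.

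Simulation agrees (15-16%). The ANOVA stays at 5%. Under linear benefit the slope test rejects in about 71% of trials against 52% for the ANOVA (rho 0.8), and 90% against 77% (rho 0.9). Part of that lead comes from the understated standard error.

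**The case against.** The best defence is that Section 10 presents its mixed model as the formal specification for primary and secondary outcomes, in between- and within-subjects vocabulary familiar from ANOVA, and that Section 12.2 powers that model. ANOVA in Section 12 would then be shorthand. The text does lean this way: only Section 12.2 calls a named model the primary analysis. But Sections 12.1 and 12.4.1 apply the ANOVA to change scores, one value per person, which is not a slope over visits. They also match the endpoint in Section 1.2.4.

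It can also be said that week number, slope and Section 6.1.2.2 together imply that weeks 2 and 4 enter. That is plausible, but it is the case in which the tests diverge.

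Section 7.11 masks analysts to arm. This limits choosing a test by its result but does not remove it, since both p-values are visible under neutral labels. Section 8.1 collects the post-intervention battery when the intervention is stopped, and Section 12.1 promises intent-to-treat. Both reduce the missing-data problem, but neither says how an absent week-6 score is handled.

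Three stronger readings are not supported:
- **That true power is about 51% and not 88%.** The SD scale of d is not stated. If d is in change-score SDs, the slope model itself has only about 56%, so setting 88% against 51% mixes scales. The 88% is unverifiable, not shown to be wrong.
- **That Holm-Bonferroni forces a stricter alpha on this test.** Section 12.1 does not define the family. It does call NeuroQOL a primary functioning measure, but Sections 1.2.4 and 10.1 make Digit Symbol Matching the sole primary outcome, which fits 0.05.
- **That naming either model is enough.** That would settle the wording, but step 4 shows that a random intercept alone may not hold 5%.

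**Conclusion.** The contradiction is certain: it rests on the text alone. Its numerical effect depends on assumptions. Under equal correlation it is modest: 3-5 power points, with the direction set by the shape of benefit; 7-12% discordant verdicts; and about 6.5% type I error if either test may be claimed. Under decaying correlation it is larger, and the random-intercept slope test is then invalid by itself at about 15-16%. The documents do not say which correlation pattern applies. Because the ambiguity falls on the trial's confirmatory test and can be removed by wording, it must be fixed.

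**What to change.** Name one primary analysis for Digit Symbol Matching, in identical words, in Sections 10, 12.1, 12.2 and 12.4.1. State which visits enter and how a missing week-6 score is handled, and label the other analysis a sensitivity analysis.

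Choose a test that targets the stated week-6 change and keeps its 5% error rate. Either the change-score ANOVA or a repeated-measures model with a week-6 contrast and unstructured covariance would serve. If a slope model is kept, add a random slope or an equivalent covariance structure to the random intercept.

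Then restate the power for the named test at the alpha that applies to it (0.05 if Digit Symbol Matching is the sole primary, as Sections 1.2.4 and 10.1 have it), giving the SD scale of d, the correlation and the visits assumed.

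The cost is protocol and SAP wording plus a re-run of the simulation, with no new data collection. The downside is that the stated power may become less favourable. The team would then have to accept a larger detectable difference at 50 per arm or revisit the sample size.

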12.3 Stratification Factors

Not applicable.

12.4 Analysis of Endpoints

12.4.1 Analysis of Primary Endpoints

Our primary cognitive measure will be change in performance on a Digit Symbol Matching Task from baseline (pre-intervention) to week 6 (post-intervention) in all participants randomized to the intervention or control arm. Our primary daily functioning measure will be change in score on the NeuroQOL Cognitive Function scale from baseline (pre-intervention) to week 6 (post-intervention) in all participants randomized to the intervention or control arm. We will use analysis of variance (ANOVA) to test for differences in Digit Symbol Matching and NeuroQOL change scores across the two arms.

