6.1.2 Treatment Phase

6.1.2.1 Week 0 (Baseline/Pre-Intervention), Week 6 (Post-Intervention), Week 12 (Post-Intervention; waitlist control participants only)

The pre- and post-intervention visits will take place at the beginning and the end of the intervention period. Participants in both arms will meet remotely with a member of the research team via a HIPAA-compliant video conferencing platform (Zoom). The full battery of cognitive tasks (~35 minutes), functional assessments (~30 minutes), and mood symptom scales (~10 minutes) will be conducted at the baseline visit. Participants in the AKL-T01 intervention arm will be trained in procedures for gameplay during this visit. (Note that the week 6 assessment session will also serve as the baseline assessment for control participants who begin the intervention following the waitlist period.)

The pre- and post-intervention assessment visits will include the following study procedures:

- **Cognitive Tasks:**
- Digit Symbol Matching

- Multiple Object Tracking
- Digit Span Backwards
- Simple RT
- Choice RT
- Letter/Number Switch
- Gradual CPT
- Visual Paired Associates
- **Functional Assessments:**
- NeuroQOL
- WHODAS (36-item)
- Modified Fatigue Impact Scale
- **Mood Symptom Scales:**
- PHQ-9
- GADS-7

6.1.2.2 Weeks 2 & 4 (\pm 2 days; *all participants*) & Weeks 8 & 10 (\pm 2 days; *waitlist control participants only*)

The intermediate assessment visits at weeks 2 & 4 (and weeks 8 & 10 for waitlist control participants) will include a shorter battery of cognitive tasks (~25 minutes) and functional assessments (~10 minutes) measuring the primary and secondary endpoints, as well as the PHQ-9 (~5 minutes) for monitoring of mood symptoms.

The intermediate assessment visits will include the following study procedures:

- **Cognitive Tasks:**
- Digit Symbol Matching
- Multiple Object Tracking
- Digit Span Backwards
- Simple RT
- Choice RT
- Letter/Number Switch
- Gradual CPT
- **Functional Assessments:**
- NeuroQOL
- WHODAS (12-item)
- **Mood Symptom Scales:**
- PHQ-9

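### The plan names two different primary analyses, a change-score ANOVA and a mixed slope model, and neither adjusts for the baseline score

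*Combined protocol and SAP*

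**What the plan says.** Section 12.4.1 takes baseline-to-week-6 change as the outcome and states: "We will use analysis of variance (ANOVA) to test for differences in Digit Symbol Matching and NeuroQOL change scores across the two arms". Section 12.1 says the same, and Section 12.4.2 extends ANOVA to the remaining cognitive tasks and the WHODAS. Section 12.1 adds: "An intent-to-treat approach will be used in for all of the analyses above".

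Section 10 (Measurement of Effect), which covers both levels of outcome, describes something else: "we will apply linear mixed effects models with fixed effects for treatment group as the between-subjects factor, time (week number) as the within-subjects factor". It adds a term for the interaction of the two. On random effects it says: "A random intercept will be included". Covariates come in only if confounders are identified: "secondary analyses will incorporate fixed terms for those putative confounders in linear models". Section 12.2 treats the mixed model as the primary analysis: "As primary analysis will utilize linear mixed models (as implemented in lme4) to examine slope of symptom change". The power statement rests on it: "For standardized beta coefficient corresponding to Cohen's d of ~0.4, power exceeds 88% (95% confidence interval 80.0-93.6%) for the base case".

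Digit Symbol Matching and NeuroQOL are collected at baseline and week 6 and also in between (Section 6.1.2.2: "The intermediate assessment visits at weeks 2 & 4"). No section puts the baseline score into the primary model as a covariate, and none gives a method for missing week-6 scores.

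**The concern.** Three things are at stake.

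- **Which test is primary.** The ANOVA and the slope model use different data and can give different p-values. The power figure supports only one of them.
- **Precision.** A raw change score subtracts the whole baseline value. Unless baseline and week 6 correlate perfectly, this removes too much and adds noise. A chance baseline difference also carries into the estimate through regression to the mean. With about 50 per arm and no stratification (Section 12.3), a difference of some size is to be expected.
- **Missing week-6 scores.** A participant without a week-6 score has no change score and leaves the ANOVA. Section 3.2 itself raises the risk of dropout in the waitlist arm, so the loss may differ between arms.

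**Working it through.** **Inputs from the documents.** 50 per arm, d about 0.4, alpha 0.05 and 100 simulated data sets (Section 12.2); visits at weeks 0, 2, 4 and 6 (Section 6.1).

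**Assumed, because the documents do not say.** Two-sided test; equal variances at all visits; the same correlation r between any two visits, taken as 0.5 to 0.8; d in baseline-SD units unless noted. Loss before week 6 is set at 0, 10 or 20%. The 20% in Section 12.2 is loss before the intervention starts, not loss of week-6 data.

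**The plan's own figure.** The interval 80.0-93.6% is the exact binomial interval for 88 successes in 100 (0.800 to 0.936), so it reflects simulation error only. A plain two-group comparison with 50 per arm and d=0.4 has 51% power (noncentral t, 98 df). The slope model reaches 88% if r is about 0.78; change-score ANOVA reaches it if r is about 0.80. So 88% is attainable for the mixed model but cannot be confirmed from the stated inputs.

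**Variance per participant of the week-6 effect, in units of the baseline variance**

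- Change-score ANOVA: 2(1-r).
- Slope model, change over 6 weeks: 36(1-r)/Sxx. For weeks 0, 2, 4 and 6 the mean is 3, so Sxx = 9+1+1+9 = 20 and the variance is 1.8(1-r). This relies on a linear course.
- ANCOVA of week 6 on baseline: 1-r².

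ANCOVA against change score: (1-r²)/[2(1-r)] = (1+r)/2, or 0.75, 0.85 and 0.90 at r=0.5, 0.7 and 0.8. ANCOVA against the slope model: (1+r)/1.8, or 0.83, 0.94 and 1.00.

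**Power.** Divide 0.4 by the square root of the variance and use the noncentral t with 50 per arm:

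| r | Change-score ANOVA | Mixed slope model | ANCOVA |
|---|---|---|---|
| 0.5 | 0.4/1.000: 51% | 0.4/0.949: 55% | 0.4/0.866: 63% |
| 0.7 | 0.4/0.775: 72% | 0.4/0.735: 77% | 0.4/0.714: 79% |
| 0.8 | 0.4/0.632: 88% | 0.4/0.600: 91% | 0.4/0.600: 91% |

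If d=0.4 is instead in SD-of-change units, change-score ANOVA has 51% and the slope model 55% at any r, while ANCOVA has 63, 57 and 55% at r=0.5, 0.7 and 0.8.

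**Baseline imbalance.** The standard error of the baseline difference is √(2/50) = 0.2 SD. A chance difference of that size shifts the expected change-score contrast by (1-r)×0.2: 0.10 SD at r=0.5 and 0.06 SD at r=0.7.

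**What weeks 2 and 4 add.** These figures use the normal approximation, which runs up to about 1 point above the t values. With complete data and r=0.6, the week-6 contrast has 70.5% power with or without weeks 2 and 4, once baseline is adjusted for. With 20% missing at week 6 and r=0.6, change-score ANOVA on completers has 51.6%, ANCOVA on completers 60.9% and the baseline-adjusted repeated-measures model 62.0%. Over r=0.5 to 0.8 and 10-20% missing, the gain from weeks 2 and 4 is 0.4 to 1.3 points.

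**The case against.** The strongest reply is that the mixed model in Sections 10 and 12.2 already answers most of this. It takes in weeks 2 and 4, keeps participants who lack a week-6 score, and is the model that was powered. That stands. A reader of Section 12.4.1 alone might infer that the intermediate data go unused and that people who miss week 6 are simply excluded. This is true of the ANOVA but not of the other written analysis. Against the slope model, baseline adjustment gains about 8 points at r=0.5 and nothing at r=0.8; at r=0.9 the slope model is slightly ahead.

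A reader might also infer that intent-to-treat cannot be delivered. The documents do not support that. Section 12.1 explains the term as including outcomes of participants who did not complete the intervention, Section 8.1 continues study procedures after the intervention stops, and Section 8.3 requires efforts to recover missed visits. An ANOVA by randomised arm keeps all of those who have a week-6 score. The gap is narrower: missing week-6 scores have no stated method.

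Nor is the baseline score thrown away, since a change score uses it with a coefficient of 1. Change-score ANOVA is valid under randomisation and matches the endpoint in Section 1.2.4. ANCOVA serves that endpoint too, because with baseline in the model the arm effect is the same whether the outcome is week 6 or change.

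The reply does not remove the conflict: the section headed as the primary analysis still says ANOVA, and the mixed model has no baseline covariate either.

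**Conclusion.** The point holds as a conflict between Sections 12.1, 12.4.1 and 12.4.2 and Sections 10 and 12.2, together with a missed gain in precision. Baseline adjustment adds about 3 to 12 points of power over change-score ANOVA for r from 0.8 to 0.5. In sample-size terms that is 1/0.90 to 1/0.75, or 11 to 33% more participants. Over the mixed slope model it adds about 8 points to none. These sizes rest on an assumed r, equal correlation between visits, and d in baseline-SD units. The direction against change-score ANOVA does not depend on the size of r, provided it is below 1.

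A reader might take the 51% for a plain comparison as proof that 88% is wrong. It is not: the figure belongs to the mixed model, whose correlation and variances are not shown. It does not carry over to the ANOVA unless r is about 0.80.

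**What to change.** In Sections 10, 12.1, 12.2, 12.4.1 and 12.4.2, name one and the same model:

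- A repeated-measures model with outcomes at weeks 2, 4 and 6; fixed effects for arm, week as a category, arm-by-week, baseline score and baseline-by-week; and an unstructured covariance. The arm difference in Digit Symbol Matching at week 6 is the single primary contrast.
- For outcomes measured with the same instrument only at weeks 0 and 6 of the randomised period, ANCOVA of week 6 on baseline. This includes the WHODAS: the 36-item form is given at weeks 0 and 6 and the 12-item form at weeks 2 and 4, so they should not be pooled as one repeated measure.
- A statement that missing scores are assumed missing at random, with a sensitivity analysis for departures from that.
- Power restated for this model, with the assumed correlation, variances and units of d shown.

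The cost is plan wording and a rerun of the power calculation; no new data are needed. Two further texts bear on intent-to-treat and are not repaired by any choice of model: Section 8.2 allows replacement of participants randomised but not treated, and Section 12.6.2 limits assessment of response to those who received the intervention. They should be reconciled with Section 12.1 at the same time.
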